5.4.1.3. Patient Global Impression of Improvement Endpoint

The PGI-I requests patients to mark the box that best describes their cluster headache condition since they started taking this medicine. The options in the displayed boxes are represented on a 7-point scale, with 1=very much better and 7=very much worse (Guy 1976).

The patient-reported PGI-I information will be captured at office visits. If the PGI-I collection date is greater than 10 days from the visit date, the record will not be used for analysis.

5.4.2. Safety Endpoints

Safety endpoints consist of the incidences of TEAEs, SAEs, and discontinuations due to adverse events (AEs), vital signs (blood pressure, pulse, and body temperature), weight, suicidal ideation and behaviors assessed by solicited questioning using the C-SSRS, ECGs, and laboratory measures (chemistry, hematology, and urinalysis).

5.4.3. Immunogenicity Endpoints

Immunogenicity endpoints consist of the incidences of antibodies to LY2951742 (ADA). An additional endpoint is the incidence of NAb present in those trial participants with ADA.

5.4.5. Pharmacokinetic Assessment

Pharmacokinetic assessment will be summarized in the pharmacokinetic/pharmacodynamic (PK/PD) SAP.

5.5. Statistical Analyses

The protocol for this study was approved on 18 December 2014. Protocol amendment (a) for this study was approved on 12 February 2015. Protocol amendment (b) for this study was approved on 22 December 2015. Protocol amendment (c) for this study was approved on 10 February 2017. The SAP Version 4 supersedes the statistical plans described in the protocol and previous versions of the SAP.

5.5.1. General Considerations

General aspects of statistical analyses are described below.

Unless otherwise specified, efficacy analyses during SP III will be conducted on an **intent-to-treat (ITT) population**, which include all patients who are randomized and receive at least 1 dose of study drug. Patients in the ITT population will be analyzed according to the treatment group that they were randomized to. Safety analyses during SP III will be conducted on the **safety population**, which also includes all patients who are randomized and receive at least 1 dose of study drug. However, patients will be analyzed by actual study treatment received most often (modal treatment) during the double-blind treatment phase. Modal treatment will be the same as randomized treatment except in some cases of incorrect treatment administration. When mean change from baseline is assessed, the patient will be included in the analysis only if he or she has a baseline and a postbaseline measurement.

Unless otherwise specified, for analyses of posttreatment phase, the **posttreatment population** will be used. **Posttreatment population** will be defined as all patients who entered the post-treatment phase (SP IV) as indicated by entering any posttreatment visit.

Statistical analysis will be carried out for the 8-week treatment phase (SP III), the 16-week post treatment phase (SP IV) as well as the 8-week treatment and 16-week post treatment phases combined (SP III/IV) as listed in [Table CGAL.5.2](#).

Safety analyses (Section [5.5.9](#)) in SP III and SP IV and analyses for exposure will be conducted based on the modal treatment group patients have received (placebo or GMB300 mg). For determining modal treatment, if there are 2 modes, then the modal treatment group will be GMB300 mg.

Unless otherwise specified, for the analyses in SP IV alone, no statistical comparisons between any treatment groups will be conducted.

Since cluster headache attack information collected through ePROs will only be collected for SP III, analyses of ePRO data will be conducted at SP III only.

Treatment effects will be evaluated based on a 2-sided significance level of 0.05 for all the other efficacy and safety analyses. The 95% confidence intervals for the difference in least-square means (LSMeans) between treatment groups will be presented. Adjustments for multiple comparisons for the analyses corresponding to the primary and gated secondary objectives are described in the sections on the primary and secondary efficacy analyses below. There will be no adjustments for multiplicity for analyses of other data.

A repeated measures analysis refers to a restricted maximum likelihood (REML)-based, mixed-effects repeated measures (MMRM) analysis using all the longitudinal observations at each postbaseline visit/week.

Categorical comparisons between treatment groups for safety measures will be performed using Fisher's exact tests, where appropriate.

Any change to the data analysis methods described in the protocol will require an amendment ONLY if it changes a principal feature of the protocol. Any other change to the data analysis methods described in the protocol, and the justification for making the changes, will be described in the SAP and/or in the clinical study report (CSR).

Additional exploratory analyses of the data will be conducted as deemed appropriate.

Statistical analysis of this study will be the responsibility of Eli Lilly and Company (Lilly) or designee. SAS® software will be used to perform most or all statistical analyses.

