10.2.1.1. Serious Adverse Events

Serious adverse event collection begins after the patient has signed informed consent and has received investigational product. If a patient experiences an SAE after signing informed consent, but prior to receiving investigational product, the event will NOT be reported as serious unless the investigator feels the event may have been caused by a protocol procedure.

Planned surgeries should not be reported as SAEs unless the underlying medical condition has worsened during the course of the study.

Study site personnel must alert Lilly or its designee of any SAE within 24 hours of investigator awareness of the event via a sponsor-approved method. If alerts are issued via telephone, they are to be immediately followed with official notification on study-specific SAE forms. This 24-hour notification requirement refers to the initial SAE information and all follow-up SAE information.

An SAE is any AE from this study that results in one of the following outcomes:

- death
- initial or prolonged inpatient hospitalization
- a life-threatening experience (that is, immediate risk of dying)
- persistent or significant disability/incapacity
- congenital anomaly/birth defect
- considered significant by the investigator for any other reason

Important medical events that may not result in death, be life-threatening, or require hospitalization may be considered serious adverse drug events when, based upon appropriate medical judgment, they may jeopardize the patient and may require medical or surgical intervention to prevent one of the outcomes listed in this definition.

Serious adverse events occurring up to and including the patient's last study visit will be collected, regardless of the investigator's opinion of causation, in the clinical data collection database and the pharmacovigilance system at the sponsor.

The investigator does not need to actively monitor patients for adverse events once the trial has ended, unless provided otherwise in the protocol. However, if an investigator becomes aware of SAEs occurring to a patient after the patient's participation in the trial has ended, the investigator should report the SAEs to the sponsor, regardless of the investigator's opinion of causation, and the SAEs will be entered in the pharmacovigilance system at the sponsor.

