12.2. Statistical and Analytical Plans

12.2.1. General Considerations

Unless otherwise specified, efficacy analyses during SP III will be conducted on an intent-to-treat (ITT) population, which include all patients who are randomized and receive at least 1 dose of IP. Patients in the ITT population will be analyzed according to the treatment group to which they were randomized. Safety analyses during SP III will be conducted on the safety population, which also includes all patients who were randomized and receive at least 1 dose of study drug. However, patients will be analyzed by actual study treatment received most often (modal treatment) during the double-blind treatment phase. When change from baseline is assessed, the patient will be included in the analysis only if he/she has a baseline and a post-baseline measurement.

For analyses of the post-treatment phase, the post-treatment population will be used. Post-treatment population will be defined as all patients who entered the post-treatment phase (SP IV) as indicated by entering any post-treatment visit.

Details related to handling of missing data will be described in the SAP.

Treatment effects will be evaluated based on a 2-sided significance level of 0.05 for all the efficacy and safety analyses unless otherwise stated. The 95% confidence intervals (CIs) for the difference in least-square means (LSMeans) between treatment groups will be presented. Adjustments for multiple comparisons for the analyses corresponding to the primary and gated secondary objectives are described in the sections on the primary and secondary efficacy analyses below. There will be no adjustments for multiplicity for analyses of other data.

Categorical comparisons between treatment groups will be performed using Fisher's exact tests, where appropriate.

Any change to the data analysis methods described in the protocol will require an amendment ONLY if it changes a principal feature of the protocol. Any other change to the data analysis methods described in the protocol, and the justification for making the changes, will be described in the statistical analysis plan (SAP) and/or in the clinical study report.

Additional exploratory analyses of the data will be conducted as deemed appropriate.

Statistical analysis of this study will be the responsibility of Eli Lilly and Company or its designee. SAS® software will be used to perform most or all statistical analyses.

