5.5.1.6. Baseline and Postbaseline Definition

Table [CGAL.5.2](#) describes the rules for determining the patient population and baseline and postbaseline observations for each study phase and type of analysis. When “last of Visit x-x” is used in the table, the last nonmissing observation obtained in the visit interval will be used.

Table CGAL.5.2. Patient Population with Baseline and Postbaseline Definitions by Study Phase and Type of Analysis

Study Phase/Analysis	Patient Population	Baseline Observation	Postbaseline Observation(s)
Study Phase III			
Continuous secondary efficacy analyses (Repeated measures)	Patients in ITT population with a baseline and at least 1 postbaseline observation	Visit 3	All Visits 4-7
TEAEs	Safety population	All Visits 1-3 before dosing	Visit 3 after dosing through Visit 7
SAEs, Discontinuations due to AEs	Safety population	NA	Visit 3 after dosing through Visit 7
C-SSRS categorical analyses	Patients in safety population with a baseline and at least one postbaseline C-SSRS assessment	Recent history: All Visits 1-3 excluding lifetime ^a All prior history: Visits 1- 3 including lifetime ^a	All Visits 3.01-7
TE abnormal laboratory values	Patients in safety population with normal laboratory values at all nonmissing baseline visits (with respect to direction being analyzed) and who have at least 1 postbaseline observation	All Visits 1-3	All Visits 3.01-7
TE immunogenicity	Patients in safety population who are evaluable for TE ADA	Visit 3	All Visits 3.01-7
TE changes in vital signs and weight, ECG parameters	Patients in safety population with a baseline and at least 1 postbaseline observation	Last nonmissing value from Visits 1-3 for BP, pulse, and ECG All Visits 1-3 for weight and temperature	Visits 3.01-7

Patient Population with Baseline and Postbaseline Definitions by Study Phase and Type of Analysis

Study Phase/Analysis	Patient Population	Baseline Observation	Postbaseline Observation(s)
Continuous safety analysis of vital signs, weight, laboratory, and ECG parameters (Box-whisker plot)	Safety population	Last non-missing value from Visits 1-3	Visits 4-7
Study Phase III and IV Combined			
TE immunogenicity	Patients in safety population who are evaluable for TE ADA	Visit 3	All Visits 3.01-9
Study Phase IV			
Post TEAEs	Posttreatment population	All Visits 1-7	All Visits 7.01-9
SAEs, Discontinuations due to AEs	Posttreatment population	NA	All Visits 7.01-9

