5.5.9. Safety Analyses

The safety analyses will be conducted for SP III in safety population and SP IV in posttreatment population.

The safety and tolerability of treatment will be assessed by summarizing the following:

- adverse events
 - treatment-emergent adverse events
 - by PT
 - by PT nested within SOC
 - by maximum severity
 - treatment-emergent adverse events by PT nested within SOC
 - adverse events leading to discontinuation by PT nested within SOC
 - adverse events of special interest
- suicide-related thoughts and behaviors by CSSRS
- vital signs and weight
- laboratory measurements
- electrocardiograms
- antibodies (ADA and Nab)

The baseline and postbaseline for all safety measures are described in [Table CGAL.5.2](#) unless specified otherwise. For SAEs, only events with a start date during the postbaseline phase will be accounted for the corresponding study phase analysis.

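### A death or SAE that starts after Visit 7 in a patient with no later visit falls in neither the SP III nor the SP IV safety tables

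*SAP*

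**What the plan says.** SAP 5.5.9 fixes the population for each phase: "The safety analyses will be conducted for SP III in safety population and SP IV in posttreatment population". SAP 5.5.1 says that the post-treatment population "will be defined as all patients who entered the post-treatment phase (SP IV) as indicated by entering any posttreatment visit", and Protocol 12.2.1 has the same rule: "Post-treatment population will be defined as all patients who entered the post-treatment phase (SP IV) as indicated by entering any post-treatment visit".

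SAP Table CGAL.5.2 (Section 5.5.1.6) sets the windows. For TEAEs, SAEs and discontinuations due to AEs, the SP III window is "Visit 3 after dosing through Visit 7" and the SP IV window is "All Visits 7.01-9". SAP 5.5.9 adds a date rule for serious events: "For SAEs, only events with a start date during the postbaseline phase will be accounted for the corresponding study phase analysis".

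SAP 5.5.1 mentions combined SP III/IV analyses, but only those listed in Table CGAL.5.2. The single combined row there is treatment-emergent immunogenicity.

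On collection, Protocol 10.2.1.1 states: "Serious adverse events occurring up to and including the patient's last study visit will be collected". Protocol 10.2.1 separately requires every AE after the first dose to be reported through the eCRF, and gives no last-visit limit.

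**The concern.** SP IV exists to follow safety after treatment stops. Entry to its tables depends on a visit record after Visit 7, not on having been dosed and having passed the end of SP III. A patient who completes Visit 7 and dies before any further contact cannot produce such a record, so the most serious outcomes are the ones least able to meet the entry rule.

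At stake is whether the post-treatment safety tables are complete. In a trial planned at about 162 patients, one missing death or SAE would matter to a reader of those tables. The C-SSRS tables give no cover: they need a postbaseline assessment, and SAP 5.5.9.1.2 treats patients without one as unevaluable. A fatal self-harm event between Visits 7 and 8 would therefore depend on the SAE tables to be seen.

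**Working it through.** The plan states no figure on this point, so there is none to reproduce. The check is one of set membership, followed by schedule arithmetic.

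**Membership.** Take a dosed patient who completes Visit 7, has an SAE or dies before Visit 8, and has no later visit of any kind.

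1. SP III tables: the window ends at Visit 7 and SAEs are placed by start date, so the event is outside.
2. SP IV tables: the event falls after Visit 7, but the patient has no post-treatment visit and is outside the population. The patient leaves both numerator and denominator.
3. Combined tables: none for AEs, SAEs or deaths.
4. Other routes in: neither SAP 5.5.1 nor Protocol 12.2.1 admits a patient through an event, a disposition date or a death date.

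The event is in neither set of tables.

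**Length of the exposed stretch** (Protocol Attachment 1: Visits 8 and 9 each 60 days after the previous office visit, allowance 8 days either way).

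- Visit 7 to Visit 8: 60 − 8 = 52 to 60 + 8 = 68 days.
- Visit 7 to Visit 9: 2 × 52 = 104 to 2 × 68 = 136 days.
- Nominal share before Visit 8: 60 / 120 = one half of SP IV.

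**Direction of any bias.** Let N patients pass SP III with E events, and let the rule exclude k of them with e events. The SP IV rate changes from E/N to (E − e)/(N − k). It falls only if e/k is greater than E/N. Excluded patients who died push it down. Patients who drift away without an event push it up. The documents give neither e nor k.

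**Illustration on assumed rates only.** Let r be the risk of such an event between Visits 7 and 8, and q the chance that a patient with one has no later visit. The expected number omitted is 162 × r × q.

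| r | q | Expected omitted |
|---|---|---|
| 0.5% | 25% | 162 × 0.005 × 0.25 = 0.2 |
| 1% | 50% | 162 × 0.01 × 0.50 = 0.8 |
| 5% | 100% | 162 × 0.05 × 1.00 = 8.1 |

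In the middle row the chance of at least one omission is 1 − (1 − 0.005)^162 = 56%. One event is 1/81 = 1.2% of a planned arm of 162 / 2 = 81. Neither r nor q comes from the documents. The figure of 162 is the planned number, and SAP Section 3 says that enrollment was stopped early, so the counts would shrink in proportion.

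**The case against.** The strongest reply is that the gap is narrow and partly covered elsewhere. Most of that stands.

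- Any post-treatment visit qualifies, and the SP IV window starts at Visit 7.01, so unscheduled visits count. Protocol 8.4.3 calls for end-of-study procedures when a patient leaves during SP IV, and an early-termination visit would plausibly count. Most AE withdrawals are therefore captured. What remains is mainly deaths, patients too ill to return and patients who refuse the termination visit.
- The database might create a visit record for a death or withdrawal. The documents do not say so.
- SP IV disposition is tabulated for ITT patients (SAP 5.5.2), and the registry SAE summary (SAP 5.9) states no phase limit. The event may appear in both. That limits the loss, but leaves outputs that would disagree with the safety tables.
- SP IV safety is descriptive (SAP 5.5.9.1), so no test and no SP III comparison changes.

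A reader might infer more than the text supports. One such inference is that the event would go uncollected because SAE collection ends at the last study visit. Protocol 10.2.1 requires all post-dose AEs on the eCRF, and Protocol 10.2.1.1 sends SAEs learned of after participation ends to the pharmacovigilance system. The two sections need reconciling, but they do not show that the event is lost. Another inference is a count of affected patients taken as a share of the 146 planned completers. The synopsis does not define completion; if it means reaching Visit 9, none of those patients is affected.

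**Conclusion.** The rule is wrong as written, with low stakes. Followed exactly, it leaves a death or SAE that starts after Visit 7, in a patient with no later scheduled, unscheduled or early-termination visit, out of both phases' safety tables. The exposure lies mainly in the 52 to 68 days before Visit 8. This conclusion assumes only that no post-treatment visit record is created by the event itself.

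It is tempting to go further and say that SP IV event rates are biased downward. That holds where excluded patients have more events than those who attend, as with deaths. It is not shown in general, because event-free patients without a later visit also leave the denominator. The size of the omission cannot be derived from the documents.

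**What to change.** For the SP IV TEAE, SAE, death and AE-discontinuation tables, define the population from SP III disposition: safety-population patients who were followed past SP III disposition or had an event after it. Set the event window by date, from the day after SP III disposition to the date of study disposition or death, and count events in it whether or not a visit followed. Alternatively, add one combined SP III/IV SAE and death table on the safety population.

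Keep the requirement for a baseline and a postbaseline value in the laboratory, ECG, vital-sign and C-SSRS tables. In Protocol 10.2.1.1, the last-visit limit on SAE collection need only be reconciled with the eCRF rule in Protocol 10.2.1.

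The cost is a few sentences of SAP text, one population flag and a date rule. SAP 5.8.1.1 already plans to rerun the SP IV analyses at final lock, so no extra analysis step is needed. The downside is a slightly larger SP IV denominator that includes some patients with short follow-up.

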5.5.1.1. Adjustments for Covariates

The repeated measures models will include the fixed, categorical effects of treatment, gender, pooled investigative site, visit/week, and treatment-by-visit/week interaction, as well as the continuous, fixed covariates of baseline value. Rules for pooling of investigative sites are described in Section 5.5.1.3. Note, in repeated measures analysis, visit will be used for measures collected at visit interval, while week will be used for all the ePRO data.

When an ANOVA model is used to analyze a continuous efficacy variable, the model will contain the main effects of treatment, gender and pooled investigative site, and appropriate baseline value included as a covariate.

The categorical, pseudo-likelihood-based repeated measures models for the visit wise/week wise binary outcomes of response will include the fixed, categorical effects of treatment, gender, visit/week, and treatment-by-visit/week interaction, as well as the continuous, fixed covariate of baseline value. Pooled investigative site was not included in the model in order to increase the likelihood of convergence.

With the exception of efficacy analyses on cluster headache attack frequency or categorical analysis of response rate (such as 50% response rate) derived from cluster headache attack frequency where the continuous value of baseline weekly cluster headache frequency will be used as covariate, all other efficacy analyses will include baseline average daily cluster headache

attack frequency category (≤ 4 vs. > 4) as a covariate in the MMRM, GLIMMIX, and ANOVA model.

5.5.1.2. Handling of Dropouts or Missing Data

Repeated measures analyses will be used as the statistical approach for handling missing data. The model parameters are simultaneously estimated using restricted likelihood estimation incorporating all of the observed data. Estimates have been shown to be unbiased when the missing data are missing at random and when there is ignorable non-random missing data (Mallinckrodt 2008). Missing at random (MAR) assumption will be evaluated using sensitivity analyses as defined in Section [5.5.11](#).

Approaches for Handling Missing Data for Derivation of Cluster Headache Attacks Derived from ePRO per 7-Day Interval

In Study CGAL, to derive the number of cluster headache attacks per 7-day interval, the daily data for each patient (including the last 7 days in the eligibility report [pre-randomization diary phase] and the 8 weeks of daily data during treatment) will be converted into 9 roughly 7-calendar day intervals: the baseline 7-day period, Weeks 1, 2, 3, 4, 5, 6, 7, and 8. Each day, the patient may have zero, 1, or multiple cluster headache attacks. For each weekly interval, the following missing data imputation method will be used:

- 1) if there are less than or equal to 3 days with nonmissing answer to cluster headache attack frequency in the weekly interval; or 2) the diary compliance rate is less than or equal to 50%, then the weekly interval will be considered missing;
- Otherwise, 1) if there are greater than or equal to 4 days with nonmissing answer to cluster headache attack frequency in the weekly interval; and 2) the diary compliance rate is greater than 50%, then the average number of cluster headache attacks across the non-missing days will be used to impute the missing days.

For detailed example about missing data imputation, please see Section [5.4.1.2](#).

Then the change from baseline to Weeks 1, 2, 3, 4, 5, 6, 7, and 8 will be derived.

The same approach will also be applied to secondary and exploratory efficacy measures that derived from ePRO data.

